**APPENDIX (vii)**

**LETTER TO THE GENERAL PRACTITIONER**

Patient Identification Number for this trial:

**Evaluation of the safety and effectiveness of the global treatment including multilayer compression therapy (Urgo KTwo®) in addition to an interactive dressing (UrgoStart® Plus in the management of venous leg ulcers**

**APPENDIX (viii)**

**WOUNDQUOL QUALITY OF LIFE QUESTIONNAIRE**

**Evaluation of the safety and effectiveness of the global treatment including multilayer compression therapy (Urgo KTwo®) in addition to an interactive dressing (UrgoStart® Plus) in the management of venous leg ulcers**

**PROTOCOL NUMBER: EUS23-4**

**IRAS ID: 327680**

**PROJECT REF NO: 23/003/GHT**

## Wound-QoL-17 questionnaire on quality of life with chronic wounds

With the following questions, we aim to find out how your chronic wound(s) affect(s) your quality of life.

Please tick one box per line !

In the last seven days ...		not at all	a little	moderately	quite a lot	very much
1	...my wound hurt					
2	...my wound had a bad smell					
3	...there was a disturbing discharge from the wound					
4	...the wound has affected my sleep					
5	...the treatment of the wound has been a burden to me					
6	...the wound has made me unhappy					
7	...I have felt frustrated because the wound is taking so long to heal					
8	...I have worried about my wound					
9	...I have been afraid of the wound getting worse or of new wounds appearing					
10	...I have been afraid of knocking the wound					
11	...I have had trouble moving about because of the wound					
12	...climbing stairs has been difficult because of the wound					
13	...I have had trouble with day-to-day activities because of the wound					
14	...the wound has limited my leisure activities					
15	...the wound has forced me to limit my activities with others					
16	...I have felt dependent on help from others because of the wound					
17	...the wound has been a financial burden to me					

**APPENDIX (ix)****SYNOPSIS OF THE CLINICAL TRIAL**

	Inclusion visit Day 0	Follow-up visits W2 / Week 4 / Week 8	Termination before W12, whatever reason	End of the study or Week 12
INVESTIGATOR				
Informed consent	X	-	-	-
Inclusion criteria validation	X	-	-	-
Exclusion Criteria validation	X	-	-	-
Ankle Brachial Pressure Index Vascular Assessment	X*	-	-	-
Wound clinical assessment	X	X	X	X
Measurement of the Wound	X	X	X	X
Photographic record	X	X	X**	X**
PATIENT				
Acceptability	-	X	X	X
Quality of Life Questionnaire	X	-	X	X

*\*ABPI to be assessed at baseline if not available in the 3 previous months.*

*\*\*A photographic record of the treated ulcer will be taken also in case of occurrence of a local adverse event.*

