### 2.2. SECONDARY OUTCOMES

The secondary criteria are to determine the following:

- Time to reach complete wound closure,
- Relative (and absolute) wound surface area reduction ( $\text{area}_{t0} - \text{area}_{t\text{last}}$ ),
- Percentage of patients with a  $\geq 30\%$  wound area reduction  $[(\text{area}_{t0} - \text{area}_{t\text{last}}) / \text{area}_{t0} \times 100]$  at Week 4 (18,19).
- Evolution of the ankle circumference,
- Patient Quality of Life through a specific the WoundQuol Questionnaire,
- The safety of the tested procedure (compression therapy system and dressings) through the nature and number of emergent local adverse events (i.e., events not present at baseline),
- Patients' acceptability of the procedure, evaluated by the investigator and by the patient,
- The change frequency per week over the treatment period.

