## 5. STUDY CONDUCT

### 5.1. Synoptic diagram of the investigation

For all included patients, the scheduled treatment duration is 12 weeks. Patients will be allocated to the Urgo K2 compression system and a wound dressing from the UrgoStart® range. Both devices must be applied according to manufacturers' recommendations as described in the respective device monographs (Appendix 1&2).

After obtaining the patient's written consent to participate and once all inclusion and exclusion criteria are met, patients will be included in the study. Patients will then be seen at Week 2 and Week 4 ± 3 days during the first month, and then every four weeks, until the 12th week for wound assessment or until complete wound closure if it happens before, with all the visits being documented in the case report form (CRF).

At each of these visits, the investigator will perform a clinical assessment and will measure the wound with a ruler, and will also take a photographic record of the venous leg ulcer.

The treatment may be discontinued, temporarily or definitively, before the required 12 weeks have been completed if the investigator deems this to be necessary: this must be then documented in the Case Report Form (CRF).

A temporary discontinuation of the tested treatment (compression system or the primary dressing) must not exceed 2 weeks; after this time, it will become a permanent discontinuation.

In case of permanent discontinuation, the investigator has to follow-up the patient until Week 12, as expected in the protocol and to treat him at his entire convenience.

The acceptability of the study treatment will also be assessed at each visit planned in the protocol.

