#### **5.4. ASSESSMENT IN THE EVENT OF STUDY WITHDRAWAL BEFORE W12**

A premature study withdrawal may occur for any of the following reasons:

- Withdrawal of informed consent,
- Healing of the tested wound; thus, the patient will have to consult the investigator as soon as possible after the onset of the wound closure to document the event and provide the exact date of the closure,
- Onset of a local adverse event requiring permanent discontinuation of the tested treatment,
- Intercurrent adverse event requiring withdrawal,
- Any other reason, to be documented.

A temporary discontinuation of the study treatment must not exceed two weeks; if it does so, it becomes a permanent discontinuation.

**In case of permanent discontinuation of the treatment (studied compression system or the interactive dressing whatever), the investigator is asked to perform the planned protocol evaluations, at the same frequency, until the final evaluation (Week 12), whatever any local treatment applied.**

On the day of permanent discontinuation, the investigator is asked:

- To make a clinical assessment,
- To measure the study lesion with a ruler,
- To make a photographic record,
- To measure the ankle circumference, in order to follow the evolution of any oedema of the lower limb, if existing.

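### The protocol contradicts itself on whether healed patients are assessed at Week 12, so the timing of the last quality-of-life value may be set by healing itself

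*Protocol*

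**What the plan says.** Section 2.2 lists "Patient Quality of Life through a specific the WoundQuol Questionnaire" as a secondary outcome, and 6.2 repeats it. Neither attaches a time point or a change score.

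The row "Quality of Life Questionnaire" in Appendix (ix) is marked at Day 0, under "Termination before W12, whatever reason" and under "End of the study or Week 12". It is blank for the Week 2, 4 and 8 visits. The form in Appendix (viii) asks about the "last seven days".

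On who is still seen at Week 12, the protocol gives two answers:

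- Section 5.1 runs visits to Week 12 or "until complete wound closure if it happens before". The photographic-record paragraph of 5.2 (numbered 1.2.5) likewise lets the treatment period finish early on healing. Section 5.4 includes healing in the list introduced by "A premature study withdrawal may occur for any of the following reasons", and adds that "the patient will have to consult the investigator as soon as possible after the onset of the wound closure".
- Section 5.5 sets a complete assessment between days 82 and 86 for all included patients. Its list covers clinical assessment, wound measurement, photograph and ankle circumference, but not quality of life.

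Section 5.4 also asks that patients who permanently stop the study treatment keep their planned evaluations up to Week 12.

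**The concern.** Where visits stop at closure, the date of the last questionnaire depends on the primary outcome: a patient who heals is measured at healing, and a patient who does not is measured at Week 12. Patients who permanently abandon the treatment are explicitly kept to Week 12, while those in whom it worked appear to be released.

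The recall period adds a second difficulty. The more promptly a healed patient attends, as 5.4 asks, the more of the seven-day window lies before closure. Items on pain, smell, discharge and treatment burden would then be rated largely on days with an open ulcer.

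With no control arm, the description from baseline to the last value is the whole quality-of-life result. If it pools several follow-up times and wound states, it has no clear reading. A statistical analysis plan can choose among collected values, but it cannot supply a Week 12 value that was never obtained.

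**Working it through.** There is no protocol figure to reproduce: quality of life has no stated target, and the 60 patients in 10.1 rest on no stated rate or precision. The check concerns timing and recall.

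**1. Gap between an early closure visit and Week 12.** Inputs are the windows in 5.3 (Week 2: days 12–16; Week 4: days 26–30; Week 8: days 54–58) and 5.5 (Week 12: days 82–86). Shortest gap = 82 − last day of the earlier window; longest = 86 − its first day; nominal = 84 − its midpoint.

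| Closure visit at | Shortest | Longest | Nominal |
|---|---|---|---|
| Week 2 | 82 − 16 = 66 | 86 − 12 = 74 | 84 − 14 = 70 |
| Week 4 | 82 − 30 = 52 | 86 − 26 = 60 | 84 − 28 = 56 |
| Week 8 | 82 − 58 = 24 | 86 − 54 = 32 | 84 − 56 = 28 |

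So an early healer's last form may precede that of a Week 12 completer by about 28 to 70 nominal days. Closure after Week 8 gives a smaller gap.

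**2. Share of the recall window before closure.** Let d be the days from closure to the closure visit. The protocol gives no number for d, so it is varied as an assumption. Open-wound share = max(0, 7 − d)/7.

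| d | 0 | 1 | 2 | 3 | 4 | 5 | 7 or more |
|---|---|---|---|---|---|---|---|
| Open-wound days | 7 | 6 | 5 | 4 | 3 | 2 | 0 |
| Share | 100% | 86% | 71% | 57% | 43% | 29% | 0% |

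The open wound makes up most of the window only for d of 3 or less, and none of it from d = 7.

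**3. How many patients.** The documents give no 12-week closure rate. The Introduction's 30–75% refers to six months; applied to 60 patients it gives 0.30 × 60 = 18 to 0.75 × 60 = 45, a loose bracket only. An assumed 50–70% closing before Week 12 would give 30 to 42. These are counts of patients whose last form could be early. The recall problem affects only those of them seen within a week of closure.

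**4. Effect of a common Week 12 form.** For closure documented by Week 8, the shortest gap is 24 days, well over 7, so the recall window at Week 12 would contain no day before that closure visit.

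**The case against.** Section 5.5 covers all included patients, and Appendix (ix) marks the questionnaire in the final column. Read together, a healed patient may well give a Week 12 form. This stands: a reader might infer that the closure-visit form is certainly the healed patient's only follow-up value, but that is one of two readings. The other does not settle the matter either, because 5.1, 1.2.5 and 5.4 point the opposite way and 5.5 omits the questionnaire.

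A reader might also infer that the protocol promises a 12-week change in quality of life. It does not. In 2.2 the reference to the treatment period belongs to change frequency. Nor is it exact that everyone unhealed answers only at Week 12: the termination column applies to any reason, and an unhealed patient who stops treatment may give both values.

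The recall argument is conditional. Visits are two to four weeks apart, closure may be noticed late, and the days just before closure concern a nearly healed ulcer rather than the baseline state. It cannot be said that healers' values in general describe the time before healing.

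Finally, every item concerns the wound, its treatment or its consequences. Weeks after closure, many answers may drop to the lowest category or reflect other ulcers on the limb, which 4.3 permits. Asking near closure is therefore defensible. This is a reason to keep that value, but not a reason against adding one at a common time.

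The study is single-arm and descriptive, with no tests (10.1), so no between-group bias or inferential error follows.

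**Conclusion.** The point holds as a contradiction that is cheap to repair. The protocol does not settle whether healed patients are assessed at Week 12, and nowhere makes clear that they complete the questionnaire then. On the reading that follow-up ends at closure, the last value comes nominally 28 to 70 days early for closure at Week 8 back to Week 2. For visits less than 7 days after closure, part of the recall covers the open wound. The pooled description would then mix follow-up times determined by the outcome and may understate quality of life after healing.

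The direction is plausible, but the size cannot be estimated because the documents contain no quality-of-life data. Any statement that a given number of the 60 end values is distorted would rest on an assumed closure rate and on every closure being seen within a week. The consequence is confined to one descriptive secondary criterion.

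**What to change.** - Reconcile 5.1, 1.2.5 (within 5.2), 5.4, 5.5 and Appendix (ix), stating plainly whether a healed patient is assessed at Week 12.
- List the questionnaire in 5.5 and in the Week 12 column of Appendix (ix) at days 82–86 for every patient, including those healed or permanently off treatment, by post or telephone if no visit takes place.
- In 2.2 and 6.2, define the quality-of-life criterion as Day 0 to Week 12.
- Keep the form at termination or closure and report it separately, with the day on which it was completed.

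The cost is one 17-item form per healed patient and a schedule amendment. There are two downsides to acknowledge: some healed patients will not return the form, although their termination value remains, and wound-specific items may bottom out or pick up other wounds once the target ulcer has closed.
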